## 7.1.2.1. Grading rules

The maximum intensity of local injection site redness/swelling will be scored at GSK Biologicals as follows using GSK Biologicals' standard grading scale based on the US Food and Drug Administration (FDA) guidelines for Toxicity Grading Scale for Healthy Adult and Adolescent Volunteers enrolled in Preventive Vaccine Clinical Trials [FDA, 2007]:

0	:	< 20 mm diameter
1	:	≥ 20 mm to ≤ 50 mm diameter
2	:	> 50 mm to ≤ 100 mm diameter
3	:	> 100 mm diameter

The investigator will assess the maximum intensity that occurred over the duration of the event for all unsolicited AEs (including SAEs) recorded during the study. The assessment will be based on the investigator's clinical judgement.

# Statistical Analysis Plan

GlaxoSmithKline

Study alias & e-track number(s): ZOSTER-063 (204928)

The intensity should be assigned to one of the following categories:

1 (mild)	= An AE which is easily tolerated by the subject, causing minimal discomfort and not interfering with everyday activities.
2 (moderate)	= An AE which is sufficiently discomforting to interfere with normal everyday activities.
3 (severe)	= An AE which prevents normal, everyday activities. Such an AE would, for example, prevent attendance at work and would necessitate the administration of corrective therapy.)

For the analysis, temperatures will be coded as follows:

Grade	Temperature
0	< 37.5°C
1	≥ 37.5°C - ≤ 38.0°C
2	> 38.0°C - ≤ 39.0°C
3	> 39.0°C

Note that fever is defined as temperature  $\geq 37.5^{\circ}\text{C}/99.5^{\circ}\text{F}$  by oral route, axillary or tympanic route, or  $\geq 38.0^{\circ}\text{C}/100.4^{\circ}\text{F}$  on rectal route.

## 7.1.2.2. Conversion of temperature to °C

The following conversion rule is used for the conversion of temperature to °C, the result is rounded to 1 decimal:

Temperature in °Celsius = ((Temperature in °Fahrenheit -32) \*5)/9

## 7.1.3. Quality of Life data

### 7.1.3.1. Calculation of study day for SF-36 and EQ-5D Assessments

Each EQ-5D and SF-36 assessment at a scheduled time point will be re-classified into time points based on the date of assessment relative to date of vaccination:

Studyday=date of assessment – date of vaccination.

To be considered evaluable at day 0 a questionnaire must have been filled in within 14 days of vaccination date. Questionnaires without a date of assessment were to be considered not evaluable. In case of two questionnaires with the same date of assessment the minimum value (i.e. the value which represents worst quality of life) of the two assessments will be selected as evaluable.

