5.3.1. Data collection

5.3.1.1. Questionnaires and Diary cards

The questionnaires (SF-36 [[APPENDIX A](#)] and EQ-5D [[APPENDIX B](#)]) and diary cards, that will be distributed and explained by the investigator or his/her delegate, are to be completed by the subject/ subject's caregiver. Any supplied questionnaires and diary cards should be preferably completed by the subject themselves.

Following vaccination, 7-day and 30-day diary cards will be dispensed to be completed by the subjects/ subjects' caregiver. The 7-day diary cards will be completed for solicited AEs (from Day 0 to Day 6 after each vaccination) and the 30-day diary cards will be completed for unsolicited AEs (from Day 0 to Day 29 after each vaccination) and any concomitant medication and vaccination taken from Day 0 to Day 29 after each vaccination (see [Table 5](#) and [Table 12](#)). These diary cards will allow a detailed characterization of the vaccine reactogenicity through a detailed collection of the occurrence of symptoms and any use of healthcare resources. Please refer to the SPM for more information on diary card and questionnaire data collection.

The questionnaires will be filled in by the subject/subjects caregiver on site at each visit. In addition, the subject/subjects caregiver will be required to complete the SF-36 PF component of the SF-36 questionnaire (i.e., items 3a to 3j, see [Table 15](#)) and the EQ-5D questionnaire at home on days 1 to 6 following each vaccination.

When the completed questionnaires and diary cards are returned to the study staff, the study staff will ask *the subject* (at the time of return or at subsequent contact) if he/she received any assistance in completing questionnaires or diary cards. If the subject had assistance completing the questionnaires and/or diary card (e.g., by a caregiver), it should be noted in the eCRF. *When questionnaires or pre-vaccination diary cards are completed at the study site, study staff can assist in reading the questions (verbatim).*
(Amended 16 November 2016)

Also, when the completed diary cards are returned to the study staff the study staff will review it together with the subject. **(Amended 16 November 2016)**

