5.5.1.4. Distribution and completion of SF-36 and EQ-5D questionnaires

Subjects /subjects' caregiver(s) will complete the SF-36 and EQ-5D questionnaires (see Sections 10.6.2.3 and 10.6.2.4). The SF-36 and EQ-5D questionnaires will be distributed to subjects at the Pre-Vaccination Visit 1. Subjects will be asked to complete both SF-36 and EQ-5D questionnaires on Day -7 (Visit 1). Completed questionnaires will be collected at Visit 1 and subject responses transcribed into the eCRF.

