5.5.2.3. Review and transcribe pre-vaccination diary cards

The investigator/study staff will ensure that subject has completed the (Visit 2) pre-vaccination diary cards prior to Vaccination 1. The investigator or designee will transcribe the information that the subject documented on the diary card prior to the visit into the eCRF.

5.5.2.4. Distribution and completion of SF-36 and EQ-5D questionnaires at Visit 2

The SF-36 and EQ-5D questionnaires will be distributed to subjects again at Visit 2. Subjects will be asked to complete the entire SF-36 and EQ-5D questionnaires on site just before vaccination at Visit 2. Completed questionnaires will then be collected and subject responses will be transcribed into the e-CRF. The same procedure for questionnaires will be followed at Visit 4 (see Section [5.5.2.11](#)).

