5.5.2.11. Distribution and completion of SF-36 and EQ-5D questionnaires post-vaccination

The SF-36 PF component of the SF-36 questionnaire (only questions 3a through 3j, see [Table 15](#)) and EQ-5D daily questionnaires will be distributed to the subjects to take home following both vaccinations at Visit 2 and Visit 4. These questionnaires will need to be completed on a daily basis (Days 1 to 6) and must be returned at the next visits (Visit 3 and Visit 5). Additionally, during Visits 3 and 5, subjects will be asked to once again fill in the entire SF-36 and EQ-5D questionnaires on site. Completed questionnaires, collected at Visits 3 and Visit 5, will be transcribed into the eCRF (see Sections [10.6.2.3](#) and [10.6.2.4](#)).

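### SAP 7.1.3.1 makes every undated questionnaire non-evaluable, with no visit-date fallback for forms completed on site, whose day is recoverable (minor)

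*SAP*

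**What the plan says.** SAP 7.1.3.1 assigns time points by date. Each SF-36 or EQ-5D assessment "will be re-classified into time points based on the date of assessment relative to date of vaccination", with study day equal to the assessment date minus the vaccination date. It then sets the rule at issue: "Questionnaires without a date of assessment were to be considered not evaluable". It draws no distinction between on-site and home forms and names no substitute date.

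The protocol fixes where the forms are completed:

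- Section 5.3.1.1, all visits: "The questionnaires will be filled in by the subject/subjects caregiver on site at each visit".
- Section 5.5.1.4, Day -7: "Completed questionnaires will be collected at Visit 1 and subject responses transcribed into the eCRF".
- Section 5.5.2.4, Day 0: "Subjects will be asked to complete the entire SF-36 and EQ-5D questionnaires on site just before vaccination at Visit 2". Visit 4 (Day 60) follows the same procedure. Section 5.5.2.8 adds that if vaccination is postponed, questionnaire completion moves with it to the day of vaccination.
- Section 5.5.2.11, Days 7 and 67: "during Visits 3 and 5, subjects will be asked to once again fill in the entire SF-36 and EQ-5D questionnaires on site". The same section limits the home forms (Days 1 to 6) to SF-36 items 3a to 3j and the EQ-5D.

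Three SAP rules determine what a lost form costs:

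- **Baseline (7.2.3).** Dose 1 uses whichever pre-vaccination form remains. The dose 2 baseline is missing only if at least two of its three forms are missing.
- **Role Physical (4.2).** The endpoint is the change from baseline to the Day 7 score.
- **QALY (7.1.3.4).** The area under the curve is calculated however many post-dose assessments exist, and is subtracted from a baseline of seven times the mean pre-vaccination utility.

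**The concern.** A blank date makes a form unusable only if its day cannot be established by other means. For the five on-site forms it can. The visit has a date, and for Days 0 and 60 that date is by protocol the vaccination date from which study day is counted. Discarding such a form loses an observed score and gains nothing in validity. Elsewhere the SAP is more lenient with incomplete dates: 7.1.2 imputes a missing day of the month for events.

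What is at stake differs by endpoint. Baseline has redundant forms and a stated fallback. Day 7 and Day 67 have neither for Role Physical, because the home forms do not carry its items. For QALY, the Day 7 form closes the curve, and no adjustment is described when it is absent and no later assessment exists.

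**Working it through.** **Inputs.** From Protocol 10.3: SD of PF change 21.2, precision 2.2, 360 evaluable, 10% non-evaluable, 400 enrolled. The confidence level is not stated; I take the precision as a two-sided 95% half-width. The share *u* of on-site forms without a date is not given. I assume 1%, 2%, 5% and, as an extreme, 10%, independent across visits.

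**Plan's own figure.** 1.96 × 21.2 / √360 = 2.190, which rounds to 2.2. In reverse, (1.96 × 21.2 / 2.2)² gives 357, close to 360. Then 360 / 0.90 = 400. The sample size reproduces and does not depend on the date rule.

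**Baseline and Role Physical.**

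- Dose 1 baseline lost (both forms undated): u²
- Dose 2 baseline lost (two or more of three undated): 3u²(1−u) + u³
- Dose 1 Role Physical change lost (Day 7 form or baseline lost): 1 − (1−u)(1−u²)

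Expected number lost out of 400:

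| u | Dose 1 baseline | Dose 2 baseline | Dose 1 Role Physical |
|---|---|---|---|
| 1% | 0.04 | 0.1 | 4.0 (1.0%) |
| 2% | 0.16 | 0.5 | 8.2 (2.0%) |
| 5% | 1.0 | 2.9 | 20.9 (5.2%) |
| 10% | 4.0 | 11.2 | 43.6 (10.9%) |

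**Primary PF precision.** With 360(1−u²) subjects, the half-width is 1.96 × 21.2 / √359.1 = 2.193 at u = 5%, and 1.96 × 21.2 / √356.4 = 2.201 at u = 10%, against 2.190 with no loss.

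**QALY.** Take a constant utility Y, so there is no true change. The Step 2 formula sums the six one-day intervals from Day 1 to Day 7.

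- Day 7 form kept: 7Y − 6Y = Y
- Day 7 form undated, Days 1 to 6 present: 7Y − 5Y = 2Y

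The subject's computed weekly loss rises by Y. At Y = 0.90 it goes from 0.90 to 1.80; for Y from 0.80 to 1.00 the rise is 0.80 to 1.00. If the sum starts at Day 0, as the worked example in SAP Table 5 does, the loss goes from 7Y − 7Y = 0 to 7Y − 6Y = Y, so the rise is the same. Averaged over subjects at Y = 0.90, the shift is 0.90u: 0.009, 0.018, 0.045 and 0.090 for u = 1%, 2%, 5% and 10%.

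**The case against.** The strongest reply is that the rule may almost never touch an on-site form. The SAP says only date of assessment. Protocol Table 5 lists transcription of the visit questionnaires by site staff as an eCRF-documented step, and 5.3.1.1 refers to the Study Procedures Manual, not available here, for how questionnaire data are collected. If the eCRF takes the assessment date from the visit, on-site forms will rarely be undated. Nothing in the documents excludes this. It makes the rate unknown and perhaps very small, but it does not supply the missing fallback.

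The baseline is already protected by SAP 7.2.3, which stands in full. The QALY jump comes from Step 2 having no adjustment for an absent Day 7 value. That is a separate weakness; the date rule only adds avoidable cases of it. Role Physical is a secondary endpoint in a study that Protocol 10.7 calls descriptive, which also stands.

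The existing checks do not settle the matter. Compliance (SAP 6.2.1.1) counts completed questionnaires without saying whether undated ones count. The analysis requiring four of seven days (SAP 6.2.3) can only exclude subjects, not restore a form.

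For home forms the rule is defensible. They have no visit date, and the SAP deliberately classifies by actual date instead of the scheduled label, so an undated home form cannot be verified as belonging to its day.

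**Conclusion.** The point holds as a minor one. SAP 7.1.3.1 would needlessly discard an on-site score if its date were missing. The consequence for primary PF precision is negligible. For Role Physical it is about 1%, 2% or 5% of subjects per dose at undated rates of 1%, 2% or 5%. For QALY it is a spurious extra loss of about one day's utility in each affected subject. These sizes rest on assumed, independent undated rates and, for QALY, on constant utility, Days 1 to 6 present and no later assessment.

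Three stronger readings are tempting and are not supported:

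- **That observed baseline and Day 7 scores are in fact being thrown away, because subjects write the date by hand.** Neither document says who enters the date or how, and neither gives a number of undated forms. The loss is conditional.
- **That the loss should be counted over all seven post-dose forms and set against the 10% non-evaluable allowance.** Six of the seven are home forms, to which the visit-date argument does not apply, and losing one day does not make a subject non-evaluable.
- **That undated home forms should also be rescued.** Their day cannot be confirmed from the documents, so excluding them is a reasonable prespecified choice.

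**What to change.** Replace the sentence in SAP 7.1.3.1 with: *An undated questionnaire completed on site takes the date of the visit at which it was collected; an undated home questionnaire is not evaluable.* Flag the on-site forms dated this way so that their number can be reported.

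The visit date gives the actual study day even when Visit 3 or 5 falls on Day 8, 9 or 10, as Protocol Table 6 allows, so the interpolation in SAP 7.1.3.4 then works as it would for a dated form. State the source of the assessment date in the same place. If the eCRF already fills it from the visit, saying so closes the point.

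The cost is one extra derivation rule and one flag. No new data are collected, and the sample size and primary estimand do not change.

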⁵ Only for women of child-bearing potential. A serum pregnancy test instead of a urine pregnancy test should only be considered if required by local or ethics committee regulations (see Section 5.5.2.6).

CONFIDENTIAL

204928 (ZOSTER-063)
Protocol Amendment 2 Final

⁶ Pre-vaccination temperatures should always be recorded orally at study sites. In rare situations when there is no other alternative, the temperature may be recorded by other route. If the temperature is taken by another route (axillary, rectal or tympanic), the route should be documented.

⁷ The post-vaccination 2 diary cards for daily recording of unsolicited AEs and concomitant medication/vaccination (Days 0-29) by subjects will be returned by mail.

⁸ SAEs related to study participation or GSK concurrent medication/vaccine are to be recorded from the time the subject consents to participate in the study.

Time intervals between study visits/contact related to study procedures performed in subjects participating in the study are presented in [Table 6](#).

Table 6 Intervals between study visits

Interval	Optimal length of interval ¹	Allowed interval (range in days)
Visit 1 (Day -7) → Visit 2 (Month 0)	7 days	7 – 10 ²
Visit 2 (Month 0) → Visit 3 (Day 7) ³	7 days	7 – 10
Visit 2 (Month 0) → Visit 4 (Month 2)	60 days	49 – 83
Visit 4 (Month 2) → Visit 5 (Day 67) ³	7 days	7 – 10
Visit 4 (Month 2) → M3 Contact (Month 3)	35 days ⁴	30 – 60
Visit 4 (Month 2) → M8 Contact (Month 8)	150 days	120 – 180
Visit 4 (Month 2) → Study conclusion M14 Contact (Month 14)	365 days	335 – 395

¹ Whenever possible the investigator should arrange study visits within this interval.

² This interval can be extended up to 14 days if subject is not able to be vaccinated at Visit 2 and needs to be rescheduled.

³ Visit 3 at Day 7 is defined as 7 days post dose 1 at Visit 2 (Month 0) and Visit 5 at Day 67 is defined as 7 days post dose 2 at Visit 4 (Month 2).

⁴ The Month 3 contact will occur when the post-vaccination 2 (Days 0-29) diary cards have been received by site (returned by mail).

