5.5.2.8. Study vaccine administration

- After completing all prerequisite procedures prior to vaccination, one dose(s) of HZ/su study vaccine will be administered IM in the deltoid of the non-dominant arm (refer to Section [6.3](#) for detailed description of the vaccine administration procedure). If the investigator or delegate determines that the subject's health on the day of administration temporarily precludes vaccine administration, the visit will be rescheduled within the allowed interval for this visit (refer to [Table 6](#) for visit intervals). In that case, all activities that need to be performed on the day of vaccination (e.g., pregnancy test, questionnaires completion, ...) will also have to be postponed until vaccination day.
- The subjects will be observed closely for at least 30 minutes following the administration of the vaccine(s), with appropriate medical treatment readily available in case of anaphylaxis.
- Any subjects with an event of HZ between Visit 1 (Day -7) and any dose of HZ/su vaccine should not receive the upcoming dose(s) of the HZ/su vaccine.

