## 6.2.1.2. Baseline Values

Baseline for dose 1 is defined as the mean of the assessments at day -7 and day 0. Dose 2 baseline is defined as the mean of the three assessments at day -7, day 0 and day 60 (day 0 for dose 2). See section [7](#) for further details.

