##### **Step1**

The baseline or reference value will be calculated from the assessments at day -7 and day 0 for dose 1 and the assessments at day -7, day 0 and day 60 for dose 2. For dose 1 the mean of the two assessments at day -7 and day 0 will be calculated. This value will then be assumed to have been the utility in the 7 days pre vaccination dose 1. Note that if vaccination dose 1 occurred more than 14 days after the scheduled day -7 then the EQ-5D assessment will not be used and the baseline utility score will be based on the value at day 0 only. To summarise:

Dose 1 : Baseline utility=7\*mean(Day -7 utility, Day 0 utility)

Dose 2 : Baseline utility=7\*mean(Day -7 utility, Day 0 utility, Day 60 Utility)

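### The SAP keeps the worse of two same-date questionnaires, a biased rule whose direction depends on whether the duplicate falls at baseline or after the dose

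*SAP*

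**What the plan says.** SAP 7.1.3.1 assigns every SF-36 and EQ-5D form to a study day by "Studyday=date of assessment – date of vaccination". For two forms with the same date, "the minimum value (i.e. the value which represents worst quality of life) of the two assessments will be selected as evaluable". The rule covers all assessments, before and after vaccination, and no reason is given. The same section adds: "To be considered evaluable at day 0 a questionnaire must have been filled in within 14 days of vaccination date".

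The selected scores then enter two averages. SAP 6.2.1.2 states: "Baseline for dose 1 is defined as the mean of the assessments at day -7 and day 0". The dose 2 baseline is the mean of three forms (Day -7, Day 0 and Day 60). The post-dose value for the primary endpoint is the mean over Days 1 to 7 (SAP 4.1). If one of the two dose 1 baseline forms is missing, the other stands alone (SAP 7.2.3).

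On timing, Protocol 5.5.2.4 says: "Subjects will be asked to complete the entire SF-36 and EQ-5D questionnaires on site just before vaccination at Visit 2". The same procedure applies at Visit 4. Protocol 5.5.2.11 has the daily take-home forms handed out at Visits 2 and 4 after vaccination, for completion on Days 1 to 6, with a full on-site form at Visits 3 and 5.

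**The concern.** The minimum of two measurements of the same quantity lies, on average, below that quantity. A worst-value convention can be defended in a trial with a success criterion, where it guards against a favourable false claim. Here Protocol 10.7 sets no success criterion and calls the analyses descriptive. The product is an estimate of change, and the rule shifts that estimate. Because the outcome is a difference, the sign of the shift depends on where the duplicate occurs.

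Two routes to a duplicate can be foreseen:

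- **Visits 3 and 5.** These may fall 7 to 10 days after the dose (Protocol Table 6). A take-home form completed late, on the visit date, ties with the on-site form.
- **Day 0 and Day 60.** The subject leaves with questionnaires due from Day 1 and a diary card that starts on Day 0. A subject who starts both that evening creates a second form with the vaccination date. The dates tie, and if function has already dropped, the rule keeps the post-injection score as baseline. Part of the loss the study is meant to measure then disappears.

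The sensitivity analyses in SAP 6.2.3 address unrelated adverse events and completeness of forms. Neither varies the duplicate rule.

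**Working it through.** **Plan's own figure (Protocol 10.3).** With SD of change 21.2 and n = 360, the 95% half-width is 1.96 × 21.2 / √360 = 2.19, which agrees with the stated 2.2. Enrolment is 360 / 0.9 = 400. The issue here is bias, so neither number changes.

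**Weight of one form in a subject's Physical Functioning (PF) change.**
- One post-dose day: 1/7, if all seven days are present.
- One dose 1 baseline form: 1/2, or 1 if the other is missing.
- One dose 2 baseline form: 1/3, if all three are present.

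**Fixed-gap calculation.** Assume the two forms differ by 10 PF points. The minimum lies 10/2 = 5 points below their mean. It also lies 5 points below the on-site form on average, if either form is equally likely to be the lower. Assume 1% to 10% of subjects are affected.

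| Duplicate falls on | Shift per affected subject | Shift in group mean, 1% to 10% | Effect on estimated loss |
|---|---|---|---|
| One post-dose day | 5/7 = 0.71 | 0.007 to 0.071 | too large |
| One dose 1 baseline form | 5/2 = 2.5 | 0.025 to 0.25 | too small |
| One dose 2 baseline form | 5/3 = 1.67 | 0.017 to 0.167 | too small |

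At 5% affected, the first two rows give 0.036 and 0.125. A baseline duplicate therefore has 3.5 times the effect of a single post-dose duplicate, in the opposite direction.

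**Post-injection form on Day 0.** If the later form is always the lower one, the right comparator is the pre-injection form and the whole gap is lost. For a drop D already present that evening (assumed 5 to 20 points), the shift per subject is D/2. Over 1% to 10% of subjects the group mean moves by 0.025 to 1.0, or by 0.05 to 2.0 if Day -7 is also missing in all of them. At D = 10 with Day -7 present, the range is 0.05 to 0.5.

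**Random-error version.** For two same-day scores with equal means and independent normal errors of SD s, E[min] = mean − s/√π. For s = 5, 10 and 15 this is 2.8, 5.6 and 8.5 points below the mean. The value 15 is 21.2/√2, the most the change SD allows under equal variances. At s = 15, moving the group mean by 2.2 would need 2.2/(8.46/2) = 52% of subjects with a duplicated dose 1 baseline form, or 2.2/8.46 = 26% with duplicates on all seven post-dose days.

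**Utility illustration (SAP Table 5).** If the hypothetical subject's Day 0 value of 0.85 were replaced by the Day 1 value of 0.75, the baseline would fall from 7 × (0.89 + 0.85)/2 = 6.09 to 7 × (0.89 + 0.75)/2 = 5.74. That hides 0.35 utility-days of loss.

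**The case against.** The schedule does not produce same-date pairs. Take-home forms cover Days 1 to 6, Day 7 is completed on site, and the baseline form is completed and collected before the injection. Every duplicate needs a subject to depart from instructions. The documents give neither a duplicate rate nor a same-day score difference, so all sizes above rest on assumptions. The rule is also pre-specified, and at Visits 3 and 5, where a late home form is plausible, it raises the estimated burden of the sponsor's own vaccine.

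Most of this stands, and it is why the point is minor. The conservatism argument holds only for post-dose days. At baseline the same rule lowers the estimated burden, with more weight per form.

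A reader might go further and infer from the 14-day sentence that a form dated up to 14 days after vaccination can serve as the Day 0 baseline. The documents do not support that:

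- The study-day formula in the same section labels a form dated three days later as Day 3.
- Protocol 5.5.2.4 places the form before the injection, and when vaccination is rescheduled, Protocol 5.5.2.8 says that "questionnaires completion, ...) will also have to be postponed until vaccination day".
- SAP 7.2.3 calls the baseline forms pre-vaccination assessments.
- The SAP's other 14-day limit (7.1.3.4, Step 1) looks backwards from vaccination and concerns the Day -7 form: "if vaccination dose 1 occurred more than 14 days after the scheduled day -7 then the EQ-5D assessment will not be used".

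What remains is loose wording. The sentence states no direction and, taken alone, does not identify which form is Day 0.

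**Conclusion.** The duplicate rule is biased by construction, and its sign changes between baseline and post-dose days. The size is small. Under an assumed 10-point gap and 1% to 10% of subjects affected, it is about 0.01 to 0.07 PF points for one post-dose day and 0.03 to 0.25 for a dose 1 baseline form. If the tie is always with a lower post-injection form, the latter becomes 0.05 to 0.5. All are well below the precision of 2.2. Only an extreme combination comes close, at 2.0: 10% of subjects affected, a 20-point drop by that evening, and Day -7 missing in each of them. Nothing in the documents suggests that. The primary conclusion is not threatened. The rule merits changing because a neutral one costs almost nothing. The 14-day sentence is an ambiguity to tidy, not a demonstrated source of bias.

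**What to change.** Replace the minimum rule in SAP 7.1.3.1 with the following:

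- On visit days, use the scheduled on-site form; at Visits 2 and 4 this is the one completed before injection.
- On other days, use the mean of the two same-date scores.
- Report the number of same-date duplicates by study day.

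A mean would not be enough at Visits 2 and 4, because it would still mix a post-injection score into the baseline.

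One further sentence should state that the Day 0 and Day 60 assessments are the on-site forms completed at the vaccination visit before injection. It would not help to redefine Day 0 as any form dated up to 14 days before vaccination. Visit 1 normally precedes Visit 2 by 7 to 10 days, and the footnote to Protocol Table 6 adds: "This interval can be extended up to 14 days if subject is not able to be vaccinated at Visit 2". Such a window would let the Visit 1 form fill both baseline slots.

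The cost is three or four sentences in the SAP, with no new data and no change in sample size. Protocol Table 5 already lists transcription of on-site and daily forms separately, and the on-site SF-36 is the full form whereas the take-home form has items 3a to 3j only.
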